3.9.4.2 Platelets

The number and percentage of patients falling in each of the following categories (using available central and local laboratory assessments) based on post-baseline assessments will be provided:

- Platelet count decrease - Grade 1a [$\geq 100 \times 10^9/L$ to < $140 \times 10^9/L$]
- Platelet count decrease- Grade 1b [$\geq 75 \times 10^9/L$ to < $100 \times 10^9/L$]
- Platelet count decrease- Grade 2 [$\geq 50 \times 10^9/L$ to < $75 \times 10^9/L$]
- Platelet count decrease- Grade 3 [$\geq 25 \times 10^9/L$ to < $50 \times 10^9/L$]
- Platelet count decrease- Grade 4 [$< 25 \times 10^9/L$]
- Maximum toxicity grade (Grade 1a , Grade 1b, Grade 2, Grade 3, Grade 4)
- Confirmed maximum toxicity grade (Grade 1a , Grade 1b, Grade 2, Grade 3, Grade 4)
- Value < $140 \times 10^9/L$
- Confirmed $\geq 30\%$ decrease from baseline
- Confirmed $\geq 50\%$ decrease from baseline
- Confirmed value < $140 \times 10^9/L$
- Confirmed value < $100 \times 10^9/L$
- Confirmed value < $75 \times 10^9/L$
- Confirmed value < $50 \times 10^9/L$
- Confirmed value < $25 \times 10^9/L$

Note that a platelet value of $140 \times 10^9/L$ is the lower limit of normal for the central laboratory. Furthermore, the platelet counts that define platelet count decrease grades are based on interactions with a regulatory authority, and align with the definitions from the the National Cancer Institute Common Terminology Criteria for Adverse Events version 4.03 (except that the CTCAE does not subdivide Grade 1 into Grade 1a and 1b).

Shift tables from baseline will be provided using the nadir value and the confirmed nadir category. Categories for the shift table will be $\geq 140 \times 10^9/L$, $\geq 100 \times 10^9/L$ to < $140 \times 10^9/L$, $\geq 75 \times 10^9/L$ to < $100 \times 10^9/L$, $\geq 50 \times 10^9/L$ to < $75 \times 10^9/L$, $\geq 25 \times 10^9/L$ to < $50 \times 10^9/L$, and < $25 \times 10^9/L$.

For each of the platelet categories investigated, time from first dose to the onset will be summarized for the patients that met the criterion using the following descriptive statistics: mean, standard deviation, median, P25, P75, and minimum and maximum. Kaplan-Meier plots for time to first event will be provided for value < $140 \times 10^9/L$ and value < $100 \times 10^9/L$.

The post-baseline nadir (absolute value, change from baseline, and percent change from baseline) of platelet count will be summarized by treatment group.

Duration of platelet counts below the $140 \times 10^9/L$ will be summarized, based on the duration (in weeks) each subject was below the $140 \times 10^9/L$.

The above analyses will be repeated for the subgroups defined by CM-ECHO Set.

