5.2 Exclusion Criteria

1. Unwillingness to comply with study procedures, including follow-up, as specified by this protocol, or unwillingness to cooperate fully with the Investigator
2. Screening laboratory results as follows, or any other clinically-significant abnormalities in screening laboratory values that would render a patient unsuitable for inclusion:
 - a. ALT/AST $> 1.9 \times$ ULN
 - b. Bilirubin $\geq 1.5 \times$ ULN (patients with bilirubin $\geq 1.5 \times$ ULN may be allowed on study following discussion with the Study Medical Monitor if indirect bilirubin only is elevated, ALT/AST is not greater than the ULN and genetic testing confirming Gilbert's disease)
 - c. Platelets $< 125 \times 10^9/L$

- d. Positive (\geq trace) for protein on urine dipstick. In the event of a positive test eligibility may be confirmed by a quantitative total urine protein measurement of < 1.0 g/24 hours
 - e. Positive (\geq trace) for blood on urine dipstick. In the event of a positive test eligibility may be confirmed with urine microscopy showing ≤ 5 red blood cells per high power field. If > 5 red blood cells per high power field and there is a clearly identifiable benign cause for the microscopic hematuria (for example chronic urinary tract infection secondary to neurogenic bladder), eligibility should be determined by discussion with the Study Medical Monitor
 - f. TSH values outside normal range (unless approved by the Study Medical Monitor)
3. Retinol level at Screen $<$ LLN
 - For patients with a TTR mutation at position 84 (e.g., Ile84Ser or Ile84Asn) and retinol $<$ LLN the exclusion criterion is signs or symptoms of vitamin A deficiency (such as evidence of vitamin A deficiency on ERG)
 4. Uncontrolled hypertension (blood pressure $> 160/100$)
 5. Positive test result for human immunodeficiency virus (HIV), hepatitis B or hepatitis C
 6. Karnofsky performance status ≤ 50
 7. Renal insufficiency as defined by estimated creatinine clearance calculated according to the formula of CKD-EPI < 60 mL/min/1.73 m² at Screen. If the calculated creatinine clearance is thought to be artificially low, a 24-hour urine creatinine clearance can be completed with prior Sponsor approval
 8. Presence of known type 1 or type 2 diabetes mellitus
 9. Other causes of sensorimotor or autonomic neuropathy (e.g., autoimmune disease)

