3.9 Safety Analyses

All safety analyses will use the Safety Set unless otherwise specified.

Safety endpoints include the following:

- Adverse events
- Vital signs and weight
- Physical examination
- Clinical laboratory tests
- Urinalysis
- ECG
- Ophthalmology and ERG examinations
- Columbia Suicide Severity Rating Scale (C-SSRS)
- Thyroid panel

- Inflammatory panel
- Coagulation
- Complement
- Immunogenicity.

For the analysis that will be performed after all patients have completed their EOT assessment, AE tables will include events with onset date up to seven days after last dose. An additional summary table of events while on-study (“summary of all TEAEs by PT and SOC”) will be created including all AEs recorded, even if onset date is more than 7 days after last dose. Unless noted otherwise, denominators for all tables will be number of subjects in the SS.

For visit based safety endpoints including laboratory assessments and vital signs, the analyses will use analysis visit windows.

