3.9.4.1 Hepatobiliary Laboratory abnormalities

The number and percentage of patients falling in each of the following categories based on post-baseline assessments will be provided:

- ALT \geq 3xULN and total bilirubin \geq 2xULN
- Confirmed ALT \geq 3xULN and confirmed total bilirubin \geq 2xULN
- ALT \geq 3xULN and international normalized ratio $>$ 1.5
- ALT \geq 3xULN and total bilirubin \geq 2xULN and ALP $<$ 2xULN
- Hepatocellular injury
- Hepatocellular injury and total bilirubin \geq 2xULN
- ALT \geq 3xULN
- ALT \geq 5xULN
- ALT \geq 8xULN
- ALT \geq 10xULN
- ALT \geq 20xULN
- Confirmed ALT \geq 3xULN
- Confirmed ALT \geq 5xULN
- Confirmed ALT \geq 8xULN
- Confirmed ALT \geq 10xULN
- Confirmed ALT \geq 20xULN
- ALT \geq 3xULN - $<$ 5xULN
- ALT \geq 5xULN - $<$ 10xULN
- ALT \geq 10xULN - $<$ 20xULN
- Total bilirubin \geq 2xULN
- ALP \geq 2xULN and baseline ALP $<$ 2xULN or baseline ALP missing
- ALT \geq 3x ULN or ALT \geq 2 x baseline
- Confirmed ALT \geq 3x ULN or confirmed ALT \geq 2 x baseline

For patients that had ALT elevation \geq 3 xULN, the time from first dose to first ALT elevation \geq 3 xULN will be summarized using the following descriptive statistics: mean, standard deviation, median, P25, P75, and minimum and maximum.

Shift tables from baseline for ALT, AST, and total bilirubin based on peak (maximum) and confirmed peak category will also be provided. Categories for the ALT and AST shift tables will be $<$ 3 x ULN, \geq 3

x ULN to < 5 x ULN, ≥ 5 x ULN to < 8 x ULN, and ≥ 8 x ULN. Categories for the total bilirubin shift table will be < 2 x ULN and ≥ 2 x ULN.

A hepatocellular injury event is defined as $(ALT/ALT\ ULN)/(ALP/ALP\ ULN) \geq 5$ and $ALT \geq 3xULN$, with the ALT and ALP assessments done on the same day. The categories listed above will also be analyzed using AST in place of ALT. For these analyses the definition of hepatocellular injury will not be changed to depend on AST.

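### The platelet outputs at the 140 threshold, including one of the two Kaplan-Meier plots, do not exclude patients who were already below 140 at baseline

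*SAP*

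**What the plan says.** All platelet counts here are in ×10⁹/L.

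- **Entry.** Protocol 5.2, exclusion 2c, removes patients with a screening count below 125. Counts of 125 to 139 are eligible.
- **Threshold.** SAP 3.9.4.2 notes that 140 "is the lower limit of normal for the central laboratory".
- **Event rule.** The same section gives the number and percentage of patients in each category, "using available central and local laboratory assessments) based on post-baseline assessments will be provided". The categories include any value below 140, a confirmed value below 140, and a Grade 1a platelet decrease (100 to below 140). None refers to the patient's baseline.
- **Timing.** Onset is summarised from first dose for each category. The section also says "Kaplan-Meier plots for time to first event will be provided for value" below 140 and below 100. The number of weeks spent below 140 is summarised too.
- **Denominator.** SAP 3.9 sets the default: "Unless noted otherwise, denominators for all tables will be number of subjects in the SS".
- **Baseline conditions elsewhere.** In SAP 3.9.4.1 the row for ALP at or above twice the ULN is limited to patients whose baseline ALP was below that level "or baseline ALP missing". SAP 3.9.5 shows QTcF increases overall and again for patients normal at baseline. Treatment-emergent adverse events (SAP 3.9.2) and the treatment-emergent C-SSRS outcomes (SAP 3.9.7) are also defined relative to the pre-dose state.

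**The concern.** The lowest platelet threshold that counts as abnormal (140) lies above the eligibility floor (125). A patient who starts at 130 and remains at 130 has had no on-study decline. Such a patient would nonetheless appear in the below-140 and Grade 1a percentages, have an onset time close to first dose, count as an early event on the Kaplan-Meier curve, and add the whole of follow-up (65 weeks on treatment alone) to the duration summary.

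Thrombocytopenia is the main safety question in this trial: Amendment 9 was prompted by severe cases, one of them with a fatal intracranial bleed. Only two platelet Kaplan-Meier plots are planned. One of them would mix counts that were low before dosing with counts that fell on study, so its early part could not be read as time to a fall in platelets.

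**Working it through.** The documents give no platelet event rate and no share of patients below 140 at baseline, so there is no planned figure to reproduce. The direction follows from the text. The size needs assumptions, which are marked as such.

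**Inputs**
- Entry floor 125 (Protocol 5.2); event threshold 140 (SAP 3.9.4.2); planned allocation 90 active, 45 placebo (Protocol 3.3).
- *b*, the share below 140 at baseline: assumed 3%, 10% and 15%, equal in the two arms in expectation because of randomisation.
- *p*, the new-onset rate among patients starting at or above 140: assumed 50% active, 10% placebo.
- *e*, the chance that a patient low at baseline has at least one post-baseline value below 140: assumed 97% active, 90% placebo. High values are plausible because Protocol 8.5.4 requires weekly counts.

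**Formula.** Reported rate = (1 − b)·p + b·e.

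For b = 10%:
- Active: 0.90 × 0.50 + 0.10 × 0.97 = 0.547, a rise of 4.7 points.
- Placebo: 0.90 × 0.10 + 0.10 × 0.90 = 0.180, a rise of 8.0 points.
- Risk difference: 54.7 − 18.0 = 36.7 points, against 50 − 10 = 40 among patients starting at or above 140.

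| b (assumed) | Low at baseline, active / placebo | Active | Placebo | Risk difference |
|---|---|---|---|---|
| 0% | 0 / 0 | 50% | 10% | 40 |
| 3% | 2.7 / 1.35 | 51.41% | 12.4% | 39.01 |
| 10% | 9 / 4.5 | 54.7% | 18.0% | 36.7 |
| 15% | 13.5 / 6.75 | 57.05% | 22.0% | 35.05 |

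**Sensitivity to *e*, at b = 10%.** If every low-baseline patient has a low value (e = 1), each arm rises by b(1 − p), which is 5 points active and 9 placebo. The risk difference is then (1 − b) × 40 = 36.0. If only 70% would have a low value anyway and the rest follow the new-onset rate, e is 0.85 and 0.73, the rates are 53.5% and 16.3%, and the difference is 37.2.

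**Sensitivity to *p*.** With new-onset rates of 40% and 10% and e = 1, the risk difference of 30 becomes 29.4, 28.5, 27.0 and 25.5 for b = 2%, 5%, 10% and 15%.

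**Effect on the curve.** Each Kaplan-Meier curve loses up to b of its patients at early draws because of counts that were low before dosing. At b = 10% that is up to 10 points in each arm.

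**Chance imbalance.** With 90 and 45 patients and b = 10%, the standard error of the between-arm difference in the low-baseline share is √(0.1 × 0.9 × (1/45 + 1/90)) = 0.055. In one trial the distortion could therefore be larger or smaller than its expected value.

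**The case against.** The strongest reply is that the rest of SAP 3.9.4.2 covers what matters clinically. It plans outputs for values below 100, 75, 50 and 25, Grades 1b to 4, confirmed falls of at least 30% and 50% from baseline, change in nadir, and a second Kaplan-Meier plot at 100. A patient who enters at 125 to 139 and stays there is an event in none of these. Its shift tables to nadir and confirmed nadir separate baseline at or above 140 from 100 to below 140, so the new-onset proportion can be read from them. Thrombocytopenia as an adverse event of special interest is compared by risk difference on events that began or worsened after first dose (SAP 3.9.2 and 3.9.2.1). All of this stands, and it confines the point to the 140 threshold. It does not repair the Kaplan-Meier plot, the onset times or the duration summary, because a shift table carries no time.

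Two further replies have weight. The ALP row is a thin precedent, since the ALT and bilirubin rows beside it carry no baseline condition. And baseline is an average of pre-dose values (SAP 3.2.1.1), so a patient averaging 141 can still cross 140 by chance; a restriction reduces non-drug events without removing them.

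A reader might infer that the same problem affects the CKD-EPI below 90 row, because entry is allowed from 60. That does not carry over. SAP 3.9.4.3 plans no Kaplan-Meier plot or onset summary for renal categories, and its shift table separates 90 and above from 60 to below 90.

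**Conclusion.** The gap is real but narrow. It affects the below-140 Kaplan-Meier plot, the below-140 and Grade 1a onset times and percentages, and the duration below 140. Both arms are raised, proportionally more where new onset is rarer, and the expected risk difference shrinks. Under the assumed new-onset rates of 50% and 10%, it falls from 40 to about 39 points at a 3% low-baseline share, about 37 at 10% and about 35 at 15%. It does not change at all if nobody was below 140 at baseline. Every one of these rates is an assumption.

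A reader might infer that the plan inflates the placebo rate alone, or that it dilutes the drug's platelet signal in general. The documents support neither: the active rate rises too, and the outputs at 100 and below, the falls relative to baseline and the adverse-event comparison are essentially unaffected. Quoting a relative risk (5.0 falling to 3.0 at the 10% share) would make the effect look larger, but SAP 3.9.4.2 plans counts and percentages, not ratios. This is an inexpensive improvement to descriptive safety displays and has no bearing on the efficacy inference.

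**What to change.** In SAP 3.9.4.2, present the below-140 Kaplan-Meier plot, the below-140 and Grade 1a onset summaries and percentages (including the confirmed row), and the duration below 140 for patients whose baseline is at or above 140 or missing, following the ALP wording. Report the number excluded in each arm. Keep the unconditioned rows beside them so that patients with the lowest starting counts stay visible. The renal section needs no change.

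The cost is SAP text and table shells, with slightly smaller denominators in the restricted rows. No new data are needed.

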3.9.4.3 Renal parameters

The number and percentage of patients falling in each of the following categories (using available central laboratory assessments) based on post-baseline assessments will be provided:

- Creatinine clearance by CKD-EPI $< 90 \text{ mL/min/1.73m}^2$
- Creatinine clearance by CKD-EPI $< 60 \text{ mL/min/1.73m}^2$
- Creatinine clearance by CKD-EPI $< 30 \text{ mL/min/1.73m}^2$
- Creatinine clearance by CKD-EPI $< 15 \text{ mL/min/1.73m}^2$
- Creatinine clearance by CKD-EPI $\geq 25\%$ decrease from baseline
- Creatinine clearance by CKD-EPI $\geq 50\%$ decrease from baseline
- Urine Alb/C ratio $> 5 \times \text{ULN}$
- Urine P/C ratio $> 5 \times \text{ULN}$
- Serum creatinine increase $> 44.2 \text{ umol/l (0.5 mg/dL)}$ from baseline
- Confirmed creatinine clearance by CKD-EPI $< 90 \text{ mL/min/1.73m}^2$
- Confirmed creatinine clearance by CKD-EPI $< 60 \text{ mL/min/1.73m}^2$
- Confirmed creatinine clearance by CKD-EPI $< 30 \text{ mL/min/1.73m}^2$
- Confirmed creatinine clearance by CKD-EPI $< 15 \text{ mL/min/1.73m}^2$
- Confirmed creatinine clearance by CKD-EPI $\geq 25\%$ decrease from baseline
- Confirmed creatinine clearance by CKD-EPI $\geq 50\%$ decrease from baseline
- Confirmed urine Alb/C ratio $> 5 \times \text{ULN}$
- Confirmed urine P/C ratio $> 5 \times \text{ULN}$
- Confirmed serum creatinine increase $> 44.2 \text{ umol (0.5 mg/dL)}$ from baseline

Shift tables from baseline for creatinine clearance by CKD-EPI will be provided using the nadir value and the confirmed nadir category. Categories for the shift table will be $\geq 90 \text{ mL/min/1.73m}^2$, $\geq 60 \text{ mL/min/1.73m}^2$ to $< 90 \text{ mL/min/1.73m}^2$, $\geq 30 \text{ mL/min/1.73m}^2$ to $< 60 \text{ mL/min/1.73m}^2$, $\geq 15 \text{ mL/min/1.73m}^2$ to $< 30 \text{ mL/min/1.73m}^2$, and $< 15 \text{ mL/min/1.73m}^2$.

The above analyses will be repeated for the subgroups defined by CM-ECHO Set.

3.9.5 Electrocardiograms

Absolute values, change and percent change from baseline in ventricular rate and ECG intervals (PR, QRS, QT, QTcF, QTcB) will be presented by treatment and visit. Shift table from baseline to the worst (highest) post-baseline value by treatment group will be used to assess the change in the QTcF

interval. The categories for the shift table will be: ≤ 450 msec, >450 msec to ≤ 480 msec, >480 msec to ≤ 500 msec, and > 500 msec. The number and percent of patients experiencing an increase from baseline in QTcF interval of greater than 30 msec or 60 msec at any time post-baseline will be summarized by treatment group. This analysis will be presented overall and also by the subgroup whose QTcF was normal at baseline. Normal QTcF will be defined as ≤ 450 msec for males or ≤ 470 msec for females. The number and percent of patients with overall qualitative ECG abnormalities will also be summarized. These analyses will be repeated for patients in the CM-ECHO Set. No statistical comparisons between treatments will be performed for these summaries.

Ventricular rate and ECG intervals (PR, QRS, QT, QTcF, QTcB), as well as treatment-emergent abnormalities, will be listed. The number and percent of patients that stopped treatment because they met a protocol-defined stopping rules for QTc prolongation will be tabulated by treatment group. This tabulation will be repeated for patients in the CM-ECHO Set.

The ECG over-read data are used to support medical monitoring and will not be used for the ECG summary and analysis. A by-patient listing of ECG over-read data will be provided.

3.9.6 *Electroretinograms (ERG) and Ophthalmology Exam*

The change from baseline in ERG results will be summarized by treatment group.

ERG results will be listed. Ophthalmology exam findings will be listed. The number and percent of patients that stopped treatment because they met a protocol defined stopping rules for ocular effects will be tabulated by treatment group.

3.9.7 *Columbia Suicide Severity Rating Scale (C-SSRS)*

The C-SSRS collects binary responses to 11 categories: five subtypes of suicidal ideation, five subtypes of suicidal behavior, and self-injurious behavior without suicidal intent. Specifically, the following outcomes are C-SSRS categories and have binary (Yes/No) responses. (The categories have been re-ordered from the actual scale to facilitate the definitions of the composite endpoints and to enable clarity in the presentation of the results.)

Suicidal Ideation:

Category 1 – Wish to Be Dead

Category 2 – Non-specific Active Suicidal Thoughts

Category 3 – Active Suicidal Ideation with Any Methods (Not Plan) without Intent to Act

Category 4 – Active Suicidal Ideation with Some Intent to Act, without Specific Plan

Category 5 – Active Suicidal Ideation with Specific Plan and Intent

Suicidal Behavior:

Category 6 – Preparatory Acts or Behavior

Category 7 – Aborted Attempt

Category 8 – Interrupted Attempt

Category 9 – Actual Attempt (non-fatal)

Category 10 – Completed Suicide

Other

Category 11 – Non-suicidal Self-injurious Behavior

In addition, a numerical score, the Suicidal Ideation Score, will be defined as the highest suicide ideation category (1–5) at which the patient responded “Yes” for the given visit. If the patient did not respond “Yes” to any of these categories, the score will be set to zero.

For each of the 11 categories above, the number and percent of patients with a “Yes” response at any time post-baseline (regardless of baseline response) will be summarized by treatment group.

In addition, treatment-emergent suicidal ideation or behavior will be summarized. Treatment emergence will be identified when the event was reported at any post-baseline visit but was not present at any baseline visit. The binary categories above and the Suicidal Ideation Score will be used to identify the following 8 composite endpoints:

- **Suicidal Ideation:** A “Yes” answer at any time post-baseline to any one of the five suicidal ideation questions (Categories 1–5), regardless of the baseline response
- **Suicidal behavior:** A “Yes” answer at any time post-baseline to any one of the five suicidal behavior questions (Categories 6–10), regardless of the baseline response
- **Suicidal Ideation or Behavior:** A “Yes” answer at any time post-baseline to any one of the ten suicidal ideation or behavior questions (Categories 1–10), regardless of the baseline response
- **Treatment-Emergent Suicidal Ideation** compared to recent history: An increase in the maximum suicidal ideation score post-baseline from the baseline suicidal ideation score
- **Treatment-Emergent Serious Suicidal Ideation** compared to recent history: An increase in the maximum suicidal ideation score to 4 or 5 post-baseline from not having serious suicidal ideation (scores of 0–3) at baseline. Only patients with a baseline score of 0–3 will be considered evaluable for this outcome.
- **Emergence of Serious Suicidal Ideation** compared to recent history: An increase in the maximum suicidal ideation score to 4 or 5 post-baseline from no suicidal ideation (score of 0) at baseline. Only patients with a baseline score of 0 will be considered evaluable for this outcome.
- **Improvement in Suicidal Ideation** compared to baseline: A decrease in the suicidal ideation score at the patient’s last C-SSRS assessment compared to the baseline assessment.

- **Emergence of Suicidal Behavior** compared to all prior history: The occurrence of suicidal behavior (a “Yes” response to one or more of Categories 6–10) post-baseline from not having suicidal behavior at baseline.

Each of the composite endpoints will be summarized by treatment group. For each treatment-emergent outcome listed, only those patients with the specified baseline condition will be considered evaluable. In addition, patients who discontinue from the study with no post-baseline C-SSRS assessment will be considered unevaluable for analyses of suicidality. Percents will be based on the number of evaluable patients for each outcome.

C-SSRS results will be listed.

4 Sample Size

The planned sample size for this study was revised from 195 to 135 using information published from the placebo controlled Phase 3 Diflunisal trial (Berk et al. 2013), a retrospective, multinational natural history study in 283 FAP patients (Adams et al. 2015), and uncontrolled data using another TTR mRNA targeted therapeutic (Adams 2015). It is estimated that the placebo group will have a 16 point increase in the mNIS+7 score from baseline to Month 15, and the treated group will have a 6.4 point increase in mNIS+7. The standard deviation of the change from baseline in each treatment group is estimated to be 14. With 135 patients (2:1 allocation ratio) there would be at least 90% power to detect a 9.6 point difference in the change from baseline in the mNIS+7 score between the 2 groups, with a two-sided t-test of 5% alpha, assuming that the dropout rate is approximately 25%. For the Norfolk QOL-DN questionnaire total score, it is estimated that the placebo group will have a 13.3 point change from baseline to Month 15, the treated group will have a 2.6 point change from baseline and the standard deviation of the change from baseline in each treatment group will be 18. With 135 patients, there would be at least 80% power to detect a 10.7 point difference in the change from baseline in the Norfolk QOL total score between the 2 groups, with a two-sided 5% alpha level, assuming that the dropout rate is approximately 25%.

5 Interim Analyses

